6.4. Analysis Populations

There will be four analysis populations.

6.4.1. Modified Intent to Treat Population

The mITT population will consist of all randomized subjects who received study product. The mITT population will be used for all primary and secondary efficacy analyses and will include subjects under the treatment to which they were randomized, regardless of compliance with the assigned treatment.

6.4.2. Per Protocol Population

The per protocol (PP) population will consist of subjects in the mITT population who complete the study without major protocol violations deemed likely to affect the primary efficacy outcome. These deviations will be classified during a blinded deviation review which will occur before unblinding the study. The PP population will be used for sensitivity analyses of the primary efficacy endpoint, including subjects under the treatment received. If the PP population

does not differ from the mITT population by more than 5%, then the sensitivity analyses with the PP population will not be done.

6.4.3. Safety Population

The safety population will consist of all subjects who received any study product. Analyses performed on the safety population will be per the study product received.

6.5. Subject Disposition

The disposition of all subjects over the course of the trial will be presented for treatment cohorts, combined lenabasum cohorts, and all subjects, using number of subjects and percentages. All percentages will be based on the number of subjects randomized.

Information will be presented on subjects who were or had: screening failures with reasons for screening failures; randomized; subjects randomized but withdrawn before dosing with reasons for withdrawal; in each analysis population; excluded from analysis populations with reasons; completed the study; discontinued from study product but continued in the study with reasons; and discontinued from study with reasons.

6.6. Protocol Deviations

Protocol deviations will be recorded in a deviation log. A blinded review of all protocol deviations will be done prior to database lock to classify the deviations into various categories and determine if they are major or minor protocol deviations, and to determine the subject exclusions from the PP analysis population.

Major protocol deviations for this study include, but are not limited to, any one of the following:

- Failure to comply with Good Clinical Practice guidelines
- Failure to meet major eligibility criteria at randomization
- Use of a prohibited concomitant medication

The number and percentage of subjects with protocol deviations will be summarized by deviation category and type (major/minor) for all treatment cohorts and the combined lenabasum cohort for the mITT population. Protocol deviations with the deviation type of “Major Protocol Violation” or “Minor Protocol Deviation” flagged will be presented in a listing.

7. DEMOGRAPHICS AND BASELINE CHARACTERISTICS

7.1. Demographics and Baseline Characteristics

The demographic and baseline characteristics variables include age (years), sex, race, ethnicity, country (United States; Non-United States), height (cm), weight (kg), BMI (kg/m²), FEV1 actual value, FEV1 % predicted value, and the number of previous PEx requiring IV antibiotics in the previous year (1; 2; 3). Subjects who record more than one race will be grouped into a single category denoted as Multi-racial. Demographic and baseline characteristics variables will be summarized by treatment cohort, the combined lenabasum group, and all subjects for the mITT, PP, and safety populations, separately. The data will also be summarized by age group (< 18 years; ≥ 18 years) for the mITT population.

7.2. General Medical History

General medical history will be coded using Medical Dictionary for Regulatory Activities, Version 22.1. The number and percentage of subjects with any general medical history will be summarized overall and by coded system organ class and preferred term. A summary table will be presented for treatment cohorts and for combined lenabasum cohort for the safety population. The data will also be presented in a listing.

If a subject reports the same preferred term multiple times within the same system organ class (SOC), the subject will only be counted once for the SOC. As with the preferred term, if a subject reports multiple conditions within the same preferred term, that subject will only be counted once for the preferred term.

7.3. CF Medical History

CF medical history data will be captured at Screening visit. Details of the CF medical history will be summarized for the safety populations in a table and presented in a listing.

The following CF medical history will be summarized for the mITT:

- Age at diagnosis (years)
- Method of diagnosis – sweat test
- CFTR genotype (mutation allele #1, mutation allele #2)
- Previous infections (*Aspergillus*, *Burkholderia cepacia*, *Mycobacterium abscessus*)
- Primary pathogenic species present (yes; no) in sputum cultures at Baseline (*Pseudomonas aeruginosa*, *Staphylococcus aureus*, *Aspergillus fumigatus*, *B. cepacia*, *M. abscessus*, *Streptococcus pneumoniae*)
- Lowest FEV1 % predicted in the last year
- Highest FEV1 % predicted in the last year
- Hemoptysis in the last year
- Number of acute PEx in the last year
- Number of acute PEx treated with IV antibiotics in the last year
- Time since last PEx requiring IV antibiotics (days), calculated as:
First dose date of study drug – date of the last PEx requiring IV antibiotics + 1
- Antibiotic(s) used prophylactically
- Other organ involvement (Pancreatic insufficiency, diabetes, sinusitis, nasal polyps)

8. TREATMENTS AND MEDICATIONS

8.1. Prior/Concomitant Medications

Concomitant medications will be coded using World Health Organization Drug Dictionary (B3, September 2019) and summarized to the therapeutic drug class (Anatomical Therapeutic Chemical [ATC] 4 classification) and preferred name. If the ATC 4 classification is not provided, the next lowest classification that is provided in the coding dictionary will be used. The preferred name will be defined as the active ingredient; if the active ingredient is not provided or includes more than two ingredients (e.g., multivitamins) then the drug name will be summarized as the preferred name. Any uncoded terms will be summarized under the ATC classification and preferred name of “Uncoded.”

Concomitant medications will be summarized using the safety population. Medications will be tabulated for each treatment cohort using number of subjects and percentages. Subjects may have more than one medication per ATC text. At each level of subject summarization, a subject will be counted once if he/she reports one or more medications.

8.2. Study Treatments

8.2.1. Extent of Exposure

Treatment exposure duration will be defined as the number of days that the subject was exposed to study treatment as calculated using the formula:

$$\text{Exposure duration (days)} = \text{date of last dose} - \text{date of first dose} + 1.$$

Last dose date will be imputed using last contact date during active treatment for the subjects lost to follow up and as the date of the last visit seen, excluding safety follow-up visit, for subjects missing last dose date.

The duration of exposure will be summarized for treatment cohorts and combined lenabasum cohort. All summaries will be based on the safety population. Summary statistics will be presented for treatment exposure.

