4.2. Study Efficacy Endpoints

4.2.1. Primary Efficacy Endpoint

The primary efficacy endpoint is the event rate of new PEx per subject per 28 weeks using the primary definition of new PEx comparing the lenabasum 20 mg BID and placebo cohorts. The event rate is based on the occurrence of new PEx, and the occurrence will be assessed during the treatment phase. It is defined as follows:

The primary endpoint will be calculated by the following for each treatment cohort:

Event rate of PEx (per subject-28 Weeks) for a treatment group is calculated as follows:

Total number of PEx using primary definition during the treatment period / [sum of subject treatment exposure durations in the treatment group (days) / 196]

[figure not shown]
Event rate of PEx (per subject) for a treatment group (without adjustment of treatment exposure) is calculated as follows:

Total number of PEx using primary definition during the treatment period / number of subjects in the treatment group

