5.1.1. Primary Definition of New Pulmonary Exacerbation

The derivation for new PEx by the primary definition is provided below. The rules for defining new antibiotics used for new PEx, including the start and stop days, are also provided below.

Primary definition of new PEx:

- Physician diagnosis of PEx
- Prescription of new antibiotics for PEx
- Start date of new antibiotics for PEx is > 28 days after the stop date of any antibiotics given for any previous PEx. The physician does not need to determine if there is > 28 days from last use of antibiotics to the new antibiotics for PEx analysis purposes. The > 28-day gap will be determined centrally
- A new PEx is not defined by the number of antibiotics prescribed or the order or route of administration of the antibiotics (oral or IV) for that new PEx
- ≥ 4 out of 12 Fuchs criteria are met

New antibiotics for PEx

- Must be given for PEx

- Must be administered by oral or IV route
- Start date is day the physician prescribes that the subject should take this antibiotic treatment for a PEx
- Stop date is the last day the physician prescribes that the subject should take this antibiotic treatment for a PEx
- Start day > Day 1
- Start day \leq Day of Visit 8 or discontinuation from the study
- Regularly given prophylactic inhaled, oral, or IV antibiotics do not count as new antibiotics unless the dose is increased or given early for a PEx

Start day of a new PEx:

The first day that the physician prescribes that the subject should take any new antibiotic treatment for that new PEx

Stop day of a new PEx:

The last day that the physician prescribes that the subject should take any new antibiotic treatment for that new PEx or day of discontinuation from the study, whichever is sooner

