8.2.2. Treatment Compliance

Study product compliance during the 28-week treatment period will be calculated for each subject by whether a subject takes all doses of study product as instructed. The number of capsules taken will be calculated by subtracting the number of capsules returned from the number of capsules dispensed during the treatment period.

The study product compliance (%) will be calculated by dividing the total number of capsules taken by the total number of capsules prescribed and then multiplying by 100. For calculations of compliance, the number of capsules prescribed will be adjusted downward if the subject was instructed not to take study capsules on certain days. Reduced dosing after Visit 8 will be excluded from the compliance calculation and summary. The formula below will be used.

Compliance (%) = [(number of capsules dispensed – number of capsules returned) / (number of days in study for which capsules were prescribed x number of capsules prescribed per day)] x 100

Study product compliance will be presented in a listing by individual and treatment cohort, with compliance presented as continuous variable. A subject will be considered compliant if the study product compliance is $\geq 80\%$ to $\leq 120\%$ of prescribed dose.

The overall study product compliance will be summarized by treatment cohorts and combined lenabasum cohort, with compliance presented as a continuous variable and as number of subjects and percentage of subjects in different categories of compliance ($< 80\%$, $80 - 120\%$, $> 120\%$), for Visits 2-8.

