9.4. Primary Efficacy Analysis

9.4.1. Event Rate of New Pulmonary Exacerbations per Subject per 28 Weeks by Primary Definition

The primary efficacy endpoint is the event rate of new PEx per subject per 28 weeks using the primary definition (Sections [4.2.1](#) and [5.1](#)), for the comparison of lenabasum 20 mg BID cohort to the placebo cohort, in the mITT population, through Visit 8 (Week 28) which is the treatment period.

The event rate per subject per 28 weeks of new PEx will be compared between the lenabasum and placebo cohorts using a Poisson regression model with effects of treatment and log (subject treatment exposure duration), adjusting for baseline subject characteristics of site location (United States; other countries), number of new PEx requiring IV antibiotics in the previous year (1; 2; 3); FEV1 % predicted (< 70; \geq 70); and baseline CFTR-targeting medications use (Yes; No – taken concomitantly on Day 1, baseline), and based on the mITT population.

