9.5.3. Time to New Pulmonary Exacerbations

Time to first new PEx (days) for subjects with a new PEx is calculated as:

Date physician initiates antibiotic(s) for first new PEx – first dose date of study drug + 1

Time to first PEx for subjects without a new PEx (days event free) is calculated as:

Date of last dose of study product during the 28-Week treatment period – first dose date of study drug + 1

For time to first new PEx analyses, a Cox-proportional hazards (regression) model will be used for comparing the covariate-adjusted difference in event-time distributions between the active and placebo cohorts. Covariates in the model will include site location (United States; Non-United States), number of new PEx requiring IV antibiotics in the previous year (1; 2; 3); FEV1 % predicted (< 70; ≥ 70); and baseline CFTR-targeting medications use (Yes; No). Hazard ratios will be provided.

A life-table method will be used to estimate survival probabilities in 14-day intervals between Day 1 to 182 plus a final interval of ≥ 183 days. Subjects at risk, number of PEx, number of

censored in each time interval and overall, survival probability in each time interval, Kaplan-Meier estimated first quartile, median and third quartile of time, hazard ratios (lenabasum/placebo) and associated 95% CI, and log-rank p-values will be provided.

The time to PEx will be evaluated using a Kaplan Meier method. The homogeneity of event time distribution will be tested between each and overall active treatment cohorts as compared to placebo using a log-rank or a weighted log-rank test (Fleming-Harrington) in case of non-parallel curves across groups.

[figure not shown]

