11.1. Adverse Events

Throughout the duration of the study, the investigator or designees will closely monitor each subject. All AEs which occur during the study, whether observed by the investigator or by the subject, and whether or not thought to be related to study drug will be recorded. The description of the AEs as recorded on the eCRF will include a description of event, start date, stopping date, intensity, if it was serious, relationship to study drug, what actions were taken with respect to the study drug, if treatment was required and the subject's outcome.

The investigator must evaluate each AE for its relationship to the study drug and for its seriousness. All AEs related to study drug must be followed until resolution or until they become stable.

AEs will be coded using Medical Dictionary for Regulatory Activities, Version 22.1.

Treatment-emergent AEs include all AEs onset between first dose and last dose of the study product, inclusive. TEAEs and AE onset during the 28-day follow-up will be summarized separately. Any AEs that occur before first dosing will be summarized in a table as Pre-Treatment AEs.

An overall summary by treatment cohort will be presented that includes the number and percentage of subjects who experienced at least one TEAE, serious TEAE, TEAEs by maximum severity, TEAEs by strongest relationship to study product, TEAEs leading to study product withdrawal, TEAE of dizziness ([Section 11.2](#)), and death. The total number of TEAEs will also be presented. The overall summary of TEAEs will also be presented by age group (< 18 years and \geq 18 years).

The number and percentages of subjects with the TEAEs listed below will be summarized by SOC, preferred term, and treatment separately. The TEAEs listed below will also be summarized by age group (< 18 years and \geq 18 years). If a subject reports the same preferred term multiple times within the same SOC, that subject will only be counted once for the SOC. As with the preferred term, if a subject reports multiple conditions within the same preferred term, that subject will only be counted once for the preferred term.

- TEAEs
- Serious TEAEs
- TEAEs leading to study product withdrawal
- TEAEs of dizziness (AE of special interest)
- TEAEs by maximum severity
- TEAEs by strongest relationship to study product
- TEAEs in \geq 2% of subjects in lenabasum 20 mg BID cohort
- TEAEs of abuse potential; relevant preferred terms include the following:

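### Treatment exposure has no Visit 8 limit, so dosing after Visit 8 enters the PEx rate denominator on days when no PEx can count

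*SAP*

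**What the plan says.** **Denominator.** Section 8.2.1 gives the only visible definition of the person-time used: "Treatment exposure duration will be defined as the number of days that the subject was exposed to study treatment as calculated using the formula", followed by date of last dose minus date of first dose plus 1. Section 4.2.1 divides the PEx count by "sum of subject treatment exposure durations in the treatment group (days) / 196". Section 9.4.1 puts the log of the same duration into the primary Poisson model, and Sections 9.4.2 and 9.5.1 reuse it.

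**Numerator.** Under Section 5.1.1 a PEx counts only if its antibiotic starts after Day 1 and no later than the "Day of Visit 8 or discontinuation from the study". Section 9.4.1 describes the analysis as running "through Visit 8 (Week 28) which is the treatment period".

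**Dosing after Visit 8.** Section 8.2.2 says "Reduced dosing after Visit 8 will be excluded from the compliance calculation and summary". No similar exclusion appears for exposure.

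**Other end dates.** Section 9.5.3 censors event-free subjects at the "Date of last dose of study product during the 28-Week treatment period". Section 13 says the efficacy and safety analyses will generally run to the end of the treatment period at Week 28, with follow-up AEs summarized separately.

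**Adverse events.** Section 11.1 states: "Treatment-emergent AEs include all AEs onset between first dose and last dose of the study product, inclusive". Section 11.2 summarizes dizziness cumulatively through Visit 8 and then in the 28-day safety follow-up. Section 2 describes that follow-up as off study product.

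**The concern.** A rate needs events and person-time from the same window. Here the event window closes at Visit 8, while the person-time of anyone still dosing afterwards does not. Each such day adds 1/196 of a subject-period with no possibility of an event.

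This looks like an omission. Section 9.5.3 limits the last dose for the time-to-event analysis. Section 8.2.1 itself limits imputed last-dose dates (last contact during active treatment, or last visit excluding the safety follow-up visit) but not recorded ones. Two subjects with identical dosing could therefore receive different exposure depending on whether the last-dose date was recorded.

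At stake are the absolute rates per 28 weeks in each arm, a primary derivation that two programmers would code the same way, and clear placement of AEs that start during dosing after Visit 8. The converse mismatch, PEx counted after product is stopped in subjects who stay in the study (Sections 4.1.12 and 9.2), is a separate matter.

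**Working it through.** **1. The plan's own figure.** Section 6.3 gives 80% power for a rate ratio of 0.65, a control rate of 0.80, two-sided alpha 0.05, and 166 per arm with about 15% dropout (166 × 0.85 ≈ 141). With a Wald test on the log rate ratio, the lenabasum 20 mg rate is 0.80 × 0.65 = 0.52 and

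power = Φ(|ln 0.65| / √(1/(141 × 0.80) + 1/(141 × 0.52)) − 1.96) = Φ(0.431/0.150 − 1.96) = 81.9%.

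This reproduces the stated 80% to within 2 points. The calculation does not involve the exposure rule, so it neither supports nor weakens the point. It supplies the design rates used below.

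**2. One affected subject.** With d dosing days after a Visit 8 at Day 196, the count is unchanged and the rate is multiplied by 196/(196 + d):
- d = 7: 196/203 = 0.97
- d = 14: 196/210 = 0.93
- d = 28: 196/224 = 0.88

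**3. A whole arm.** Let f be the share of subjects dosed after Visit 8. Both f and d are assumptions, and all other exposure is set to 196 days. Extra exposure is f × d/196, and the arm's rate becomes rate × 196/(196 + f × d).

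| f | d | Extra exposure | Placebo rate (0.80) | 20 mg rate (0.52) |
|---|---|---|---|---|
| 5% | 7 | 0.18% | 0.799 | 0.519 |
| 10% | 14 | 0.71% | 0.794 | 0.516 |
| 20% | 28 | 2.86% | 0.778 | 0.506 |
| 100% | 28 | 14.3% | 0.700 | 0.455 |

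The last row is an outer bound, not an expectation.

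**4. The rate ratio.** With exposure as an offset, the expected ratio is 0.65 × (196 + f_P × d)/(196 + f_L × d), where f_P and f_L are the shares in the placebo and lenabasum arms. If the shares are equal, it stays at 0.65.

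A simulation compared capped with uncapped exposure (500 trials per scenario, 166 per arm, same f in both arms):
- f = 10%, d = 14: mean ratio 0.6489 under both rules; 86.0% of trials significant under both.
- f = 20%, d = 28: mean ratio 0.6455 capped and 0.6456 uncapped; 89.4% significant under both.

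If the dosing fell in one arm only, f = 20% and d = 28 would give 0.65 × 196/201.6 = 0.632 (lenabasum only) or 0.65 × 201.6/196 = 0.669 (placebo only).

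**5. Adverse events.** Take an AE that starts after Visit 8 while the subject is still dosing. Under Section 11.1 it is treatment-emergent, because onset precedes the last dose. Under Section 11.2 a dizziness event would fall outside the on-treatment periods, which end at Visit 8. Section 13 would place it after the treatment period. Section 2 would not count that time as off-product follow-up. These sections do not give one answer.

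**The case against.** The strongest reply is that the plan as a whole shows where exposure should stop. Section 13 generally ends analyses at Week 28, Sections 3.1 and 4.1.7 and the 9.4.1 wording agree, and the imputation rule in 8.2.1 excludes the safety follow-up visit. This stands as evidence of intent. A general statement is not a derivation rule, however, and it does not alter the formula in 8.2.1.

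Second, dosing after Visit 8 is visible in a single sentence of Section 8.2.2. Numbering passes from 4.1.9 to 4.1.11, and text that says who receives it and for how long may have been removed. Section 4.1 gives the safety follow-up visit to completers everywhere except France, so the dosing may be confined to French sites, but this cannot be confirmed. The objection stands as to size: the shares and durations above have no source in the SAP.

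Third, a reader might infer that the primary comparison is biased. The documents do not support that. The hypothesis in Section 6.2 concerns the ratio, procedures are identical across blinded arms (Section 4.1.8), and equal dosing leaves the ratio and power essentially unchanged. The 0.632 and 0.669 figures need one-arm dosing, for which the SAP gives no basis.

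Fourth, a reader might infer that the treatment-emergent window should also stop at Visit 8, with later events moved to the post-treatment tables. That would label events arising on study product as post-treatment, although Section 2 describes the follow-up as off study product. This objection stands in full: the AE passages need reconciling, not a cut-off at Visit 8.

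**Conclusion.** The point holds as an unreconciled definition that should be corrected. Followed literally, Section 8.2.1 produces a denominator that outlasts the numerator for any subject dosed after Visit 8, and nothing in the visible text amends it.

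The consequence is a small understatement of absolute PEx rates: 0.2-2.9% too much total exposure if 5-20% of subjects have 7-28 extra days, which is an assumed range. The expected rate ratio and power are essentially unaffected unless post-Visit-8 dosing differs by arm, for example through unequal completion. For safety, the finding is limited to disagreement among Sections 11.1, 11.2 and 13 on where AEs with onset during dosing after Visit 8 belong. No view is taken on the dosing itself.

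**What to change.** 1. In Section 8.2.1, define exposure for the rate denominator and offset (Sections 4.2.1, 9.4.1, 9.4.2 and 9.5.1) as min(date of last dose, date of Visit 8) − date of first dose + 1. This follows the intent of Sections 9.5.3 and 13. Use the actual Visit 8 date rather than Day 196, because Section 5.1.1 closes the event window on that date. For subjects without a Visit 8, use the earlier of last dose and study discontinuation.
2. Report dosing days after Visit 8 separately, by arm, in the extent-of-exposure summary. This also shows whether they differ between arms.
3. Reconcile Sections 11.1, 11.2 and 13. Tabulate AEs with onset during dosing after Visit 8 as their own identified period, and keep them out of the post-treatment tables.

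The cost is a few sentences in the SAP, a one-line change to the exposure derivation and one extra AE period, all settled before unblinding. If the SAP is already signed, Section 2 allows no further sponsor change, so the clarification would be recorded in the CSR under Section 14.

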4.1.12. Discontinuation from Study Product but Continuation in Study

A subject may discontinue study product and continue in the study. If a subject permanently discontinues study product, they will be asked to continue in the study for efficacy and safety follow-up with Visits 5 and 8 performed off study product, starting with the next one of these visits that occurs after discontinuation of study product. For subjects who do not withdraw consent and agree to return for these visits, an additional 28-day safety follow-up after Visit 8 will not be done. Safety and efficacy data will be collected during these visits and included in analyses of safety and efficacy data. The impact of having these subjects remain in the study will be assessed in sensitivity analyses of the primary and first secondary efficacy outcomes.

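### The missing last-dose rule in SAP 8.2.1 can place the last dose at a visit attended off product, overstating dosing exposure and extending the treatment-emergent AE window

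*SAP*

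**What the plan says.** Section 8.2.1 defines exposure as the days on which a subject was exposed to study treatment, calculated from first to last dose inclusive. It has two rules for an unknown last dose:

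- Lost to follow-up: "Last dose date will be imputed using last contact date during active treatment for the subjects lost to follow up".
- Last-dose date missing: "as the date of the last visit seen, excluding safety follow-up visit, for subjects missing last dose date".

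Section 4.1.12 deals with subjects who permanently stop product but stay in the study: "they will be asked to continue in the study for efficacy and safety follow-up with Visits 5 and 8 performed off study product". For those who agree to return, "an additional 28-day safety follow-up after Visit 8 will not be done".

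The last-dose date is used in several places. It closes the AE window in 11.1: "Treatment-emergent AEs include all AEs onset between first dose and last dose of the study product, inclusive". It feeds the denominator of the primary rate in 4.2.1, "sum of subject treatment exposure durations in the treatment group (days) / 196", and the log-exposure term in 9.4.1. In 9.5.3 it gives the event-free time of subjects without a PEx: "Date of last dose of study product during the 28-Week treatment period – first dose date of study drug + 1".

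**The concern.** The missing-date rule excludes one visit, the safety follow-up, and subjects handled under 4.1.12 do not have that visit. The visits they do attend off product, Visits 5 and 8, are not excluded. Applied literally, the rule dates the last dose to a day when the subject is known to have been off product, which conflicts with the definition of exposure in the same section. The companion rule for subjects lost to follow-up carries a limit to active treatment, so the omission looks like a drafting gap.

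Two outputs are at stake. The extent-of-exposure summary would count off-product weeks as dosing. The TEAE tables, which report the primary safety endpoint (4.3.1), would include events that began after dosing had stopped, only because a date field was blank.

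**Working it through.** The SAP gives no count of missing last-dose dates and no stop days, so there is no plan figure to reproduce beyond the nominal period: 28 weeks × 7 = 196 days, the divisor in 4.2.1. Stop days below are assumptions.

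**Step 1. Who is affected.** All three conditions must hold: product permanently stopped, a return for Visit 5 or 8 off product, and no recorded last-dose date. If the date is recorded, 8.2.1 uses it and nothing goes wrong.

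**Step 2. Effect per subject.** Excess days = nominal day of the last visit seen − true stop day.

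| Assumed stop | Last visit seen | Counted | True | Excess | Ratio |
|---|---|---|---|---|---|
| Day 42 | Visit 8, Day 196 | 196 | 42 | 154 | 4.7 |
| Day 56 | Visit 8, Day 196 | 196 | 56 | 140 | 3.5 |
| Day 112 | Visit 8, Day 196 | 196 | 112 | 84 | 1.75 |
| Day 42 | Visit 5, Day 112 (Week 16) | 112 | 42 | 70 | 2.7 |

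**Step 3. Effect on a cohort's exposure total.** Take 166 subjects and 15% dropout (6.3), and assume completers have 196 days and dropouts a mean of 98.

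- Total: 166 × (0.85 × 196 + 0.15 × 98) = 166 × 181.3 ≈ 30,096 days.
- One affected subject with a Day 42 stop: 154 / 30,096 = 0.5%.
- Five: 5 × 154 = 770; 770 / 30,096 = 2.6%.

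A second set of assumptions gives a similar range. Let everyone else have 196 days.

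- 1% affected, stop on Day 112: true mean 0.99 × 196 + 0.01 × 112 = 195.16; 196 / 195.16 − 1 = 0.4%.
- 5% affected, stop on Day 56: true mean 0.95 × 196 + 0.05 × 56 = 189.0; 196 / 189.0 − 1 = 3.7%.

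**Step 4. Effect on the TEAE window.** For the Day 42 stop, the window in 11.1 should close on Day 42 but closes on Day 196. Any AE starting from Day 43 to Day 196 is counted as treatment-emergent. This can only add events.

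**Step 5. Does it distort the PEx rate?** Section 5.1.1 accepts a PEx that starts up to Visit 8 or discontinuation from the study, not from product. Section 9.2 keeps off-product assessments in the primary analysis. A subject who stops on Day 42 and stays to Visit 8 is therefore observed for events over about 196 days. At the planning rate of 0.80 (6.3), 0.80 events are expected over that time. Divided by 42 days of exposure, the rate is 0.80 / (42 / 196) = 3.73 per 28 weeks; divided by 196 days, it is 0.80. For this analysis the imputed date may lie nearer the true time at risk than the true stop date does.

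**The case against.** A reader might infer that the rule lowers PEx rates, lowers AE rates per unit of exposure, and favours the 20 mg cohort. The documents support none of these.

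- **PEx rates and event-free time.** Step 5 shows that treating the early stop date as the correct denominator sets a short denominator against a long event window. A longer denominator is not shown to be the wrong one.
- **AE rates per exposure.** Section 11.1 plans numbers and percentages of subjects and total TEAE counts. No exposure-adjusted AE rate appears in the text shown.
- **Imbalance toward 20 mg.** The SAP gives no product stops or missing dates by cohort.

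It is also fair to say that these subjects are still seen by the site, which can ask when dosing ended, so few dates may be missing. Late and incomplete data entry and reduced source verification during COVID-19 (4.1.14) make missing dates plausible but do not count them.

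Finally, Section 13 describes on-treatment analyses running to Week 28, or to discontinuation for subjects who leave the study early, and 9.2 includes off-product safety assessments. One could argue that a window to Week 28 was intended. But 11.1 closes the TEAE window at last dose. Two subjects who stop on the same day and both return for Visit 8 would get 42 or 196 days depending only on whether a field was filled in. That inconsistency stands under either intention.

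**Conclusion.** The point holds in limited form. For subjects without a recorded last-dose date who stopped product and returned for Visit 5 or 8, the rule as written gives a wrong dosing exposure and too long a TEAE window, and nothing else in the SAP caps the imputed date. The error can be large for one subject (154 days in the Day 42 example) and is probably small for a cohort: about 0.4% to 3.7% of exposure across the assumptions above. Those figures rest on assumed stop days and numbers affected. No bias in the primary PEx comparison or in time to first PEx is established. What the PEx analyses do need is follow-up time that matches their event window for every product stopper, whether or not the last-dose date is recorded.

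**What to change.** In 8.2.1, reword the missing-date clause for the exposure summary and the TEAE window. A missing last-dose date becomes the last visit or contact while the subject was still on product, as the lost-to-follow-up clause already does. It is capped at any recorded date of product discontinuation and is never a Visit 5 or 8 attended off product under 4.1.12. The cap should be optional: 6.5 shows that product discontinuation and its reasons are tabulated, but not that a separate date is collected.

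State separately, in 4.2.1, 9.4.1 and 9.5.3, that follow-up time for the PEx analyses runs to the end of the event window in 5.1.1 for all product stoppers. Without that sentence, the corrected exposure date would shorten the PEx denominator for the affected subjects.

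The cost is one clause in 8.2.1 and one sentence on PEx follow-up time. Affected subjects can be listed blind from the disposition data. Section 2 rules out sponsor changes after signature, so the edit belongs before signing; if that has passed, Section 14 sends the change to the CSR.
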